### **6.4. Unscheduled Visits**

Unscheduled visits may be performed at any time during the study whenever necessary to assess for or follow-up on adverse events, at the patient's request, or as deemed necessary by the investigator. The date and reason for the Unscheduled visit should be recorded in the source

documentation. The following activities should be completed at Unscheduled visits: recording of reason for the visit, concomitant medication review, and evaluation of adverse events. In addition, procedures such as vital signs, weight, complete physical examination, sign- and symptom-directed physical examination, clinical laboratory assessment, urinalysis, urine pregnancy testing, pharmacodynamic sampling, mammogram (for women  $\geq 40$  years old), 12-lead ECG, study drug compliance and dispensation, eDiary review, dispensation or prescription of protocol-specified analgesics, etc, may be conducted as needed. See the Schedule of Activities (Section 1.1) for tests that may be performed, as indicated at an Unscheduled visit. The investigator should consult with the medical monitor, if needed, to discuss Unscheduled visit testing. The investigator should obtain approval from the sponsor to perform an unscheduled endometrial biopsy or DXA, unless urgently indicated.

## **6.5. Study Procedures**

### **6.5.1. Efficacy-Related Procedures**

#### **6.5.1.1. Pharmacodynamics Sample Collection**

A blood sample for the pharmacodynamic analysis of serum estradiol will be collected predose at the visits indicated in the study Schedule of Activities (see Section 1.1), other than at the Week 104 or the Early Termination visit, when no dose is administered. These pharmacodynamic samples will be analyzed at a central laboratory. These results will not be shared with the sites at any time.

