## 9.6. Pharmacodynamics Analyses

The change from the parent study Baseline to Week 52 and to Week 104 in predose concentrations of serum estradiol will be summarized. Percentage of patients with concentrations of serum estradiol levels < 10 pg/mL and < 20 pg/mL will be provided.

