#### Pharmacodynamic Endpoint

To be assessed at Week 52 and Week 104

- Change from parent study Baseline in predose concentrations of serum estradiol.

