Dispense or Prescribe Protocol-Specified Analgesic Drugs v	X	X	X	X	X	X	X	X	X		X h	
Treatment Compliance		X	X	X	X	X	X	X	X	X	X h	
Take Study Drug Dose in Clinic	X w					X				X	X h	
Daily Self-Administration of Study Treatment x		X ----- X										
Take Protocol-Specified Rescue Analgesics as Needed y		X ----- X										

VISIT NAME (Timing is relative to MVT-601-3101/-3102)	PERIOD											SAFETY FOLLOW-UP
	Week 24/Baseline (Week 24 of Parent Study; Baseline of Extension Study)	Week 28 and Week 32	Week 36	Week 40 and Week 44	Week 48	Week 52 a	Week 65	Week 78	Week 91	Week 104 a / Early Termination	Un- scheduled b	Follow-Up c (~30 days after last dose of study drug)
Visit Window (days)	Parent Study Day 169 -10/+20	±7	±7	±7	±7	±7	±7	±7	±7	±7	-	-3 to +18
EHP-30 Questionnaire z	X g		X		X	X		X		X	X h	
Patient Global Assessment for Pain y	X g	X	X	X	X	X	X	X	X	X	X h	
[on paper] Patient Global Assessment for Function aa	X g	X	X	X	X	X	X	X	X 	X	X h	
Patient Global Impression of Change y	X g		X			X					X h	
[on paper] EHP Work Domain z	X g					X		X		X	X h	
EQ-5D-5L Questionnaire y	X g					X		X		X	X h	
Adverse Event Collection bb	X	X	X	X	X	X	X	X	X	X	X	X
Status of Menstruation Recovery												X cc,cc
Telephone Contact dd						X (W57)	X (W71)	X (W85)	X (W98)			
Mammogram dd						X dd				X dd	X dd	

BP = blood pressure; DXA = dual-energy x-ray absorptiometry; ECG = electrocardiogram; eDiary = electronic diary; EHP = Endometriosis Health Profile; EQ-5D-5L = European Quality of Life Five-Dimension Five-Level Scale; HR = heart rate; NRS = Numerical Rating Scale; PGA = Patient Global Assessment; sB&B = Subject Modified Biberoglu and Behrman; W = week.

a The Week 52 visit should occur on or after the 1-year anniversary of Baseline Day 1 of the parent study (± 7 days), and the Week 104 visit should occur on or after the 2-year anniversary of Baseline Day 1 of the parent study.

b Unscheduled visits may be conducted at the investigator's discretion when needed. The reason for the visit will be captured in the source documents.

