- o For Week 24/Baseline samples, see the parent protocol (MVT-601-3101 or MVT-601-3102). At Week 104/Early Termination, collect a sample for analysis of estradiol concentrations only. On days when pharmacodynamics samples are collected, administer the study treatment after the pharmacodynamics sample collections are collected.
- p All women enrolled in the study will continue to use the patient eDiary dispensed in the parent study. Patients will complete daily eDiary entries, including NRS pain scores, menstruation information, analgesic drug use, date and time of study drug administration, and sB&B scale scores until Week 52. After Week 52, eDiary scores will be entered over four eDiary collection cycles on the following schedule: Week 57 to the Week 65 visit, Week 71 to the Week 78 visit, Week 85 to the Week 91 visit, and Week 98 to the Week 104 visit.
- q Bone densitometry (L1-L4, total hip, femoral neck) will be submitted for central reading.
- r See Section 6.5.2.6 for details on the timing and follow-up of bone densitometry.

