- u Please see Appendix 1 for list of protocol-specified analgesics and see the Investigator Site File for information on where and how to obtain protocol-specified analgesic medications by country. At the Week 104 visit, patients who will not be proceeding to another extension study will be re-dispensed or prescribed protocol-specified analgesic drugs, if needed, to ensure sufficient supply until the Follow-Up visit. For patients proceeding to another extension study, refer to the protocol for that next study.
- v Pregnancy test must be negative before the study drug dose is administered. For patients whose Baseline Day 1 visit is conducted on a different day than the parent study Week 24 visit, perform an unscheduled pregnancy test at Baseline Day 1 prior to administering the first dose of study drug.
- w Patients will take the first dose of the study drug for this study once daily starting with the Week 24/Baseline visit (taken at the visit). If necessary, for logistical reasons (eg, delayed availability of study drug supply on site, others), and with sponsor/designee approval, the first dose of open label study drug for MVT-601-3103 may be administered up to 10 days following the parent study Week 24/Baseline visit. If the first dose of study drug is not given during this up to 10-day interval, the parent study follow-up procedures should be followed (ie, adverse event reporting, eDiary completion, etc.). The first dose of study drug for this extension study must not be taken until all parent study Week 24 procedures such as laboratory tests have been completed. Therefore, results of testing required for eligibility (eg, DXA) must be available on or prior to the Week 24/Baseline visit. The last dose of study drug will be taken in the clinic during the Week 104/Early Termination visit.
- x Patients may only take their study-specified analgesics for pain. Analgesics should not be taken prophylactically (ie, in anticipation of pain).
- y The patient will enter her response(s) into an electronic tablet device at the site. On visits when both tablet and paper questionnaires are being performed at the site, the patient should complete the tablet questionnaires before the paper questionnaires.
- z The patient will enter her response onto a paper questionnaire at the site. Paper questionnaires should be done in the following order: PGA for function, EHP Work Domain.

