### **5.4. Directions for Administration**

All study patients will take a study treatment of one tablet and one capsule once daily.

The study treatment should be taken in the fasted state (other than water, tea, or coffee) in the morning, at least 1 hour before breakfast. If dosing is missed in the morning for any reason, the study treatment may be taken later in the day, under fasting conditions, at least 1 hour before or 2 hours after eating a meal. The study treatment should be taken as close as possible to the same time of morning each day.

On Week 24/Baseline 1, Week 52, and Week 104 clinic visit days, study drug will be administered in the clinic rather than at home (see Schedule of Activities in Section 1.1).

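### Section 6.5.1.1 lifts predose collection for the Week 104/Early Termination estradiol sample because no dose is given, while other sections give a dose at that visit and the endpoint is predose estradiol

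*Protocol*

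**What the plan says.** The file holds two protocol texts: Amendment 2, and a later one with mammography and COVID-19 guidance. The points below are in the later text unless noted.

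**Is a dose given at Week 104/Early Termination?**
- Section 6.5.1.1 has estradiol sampled predose "other than at the Week 104 or the Early Termination visit, when no dose is administered".
- Schedule of Activities, footnote w: "The last dose of study drug will be taken in the clinic during the Week 104/Early Termination visit".
- Section 5.4: "On Week 24/Baseline 1, Week 52, and Week 104 clinic visit days, study drug will be administered in the clinic rather than at home". Early Termination is not named here.
- The schedule row "Take Study Drug Dose in Clinic" is marked at Week 24/Baseline, Week 52 and Week 104/Early Termination.

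**When is the sample drawn?**
- Schedule footnote o: "At Week 104/Early Termination, collect a sample for analysis of estradiol concentrations only". It continues: "On days when pharmacodynamics samples are collected, administer the study treatment after the pharmacodynamics sample collections are collected".

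**What is analysed?**
- The pharmacodynamic endpoint, at Week 52 and Week 104, is "Change from parent study Baseline in predose concentrations of serum estradiol".
- Section 9.6, visible only in the Amendment 2 text, states: "The change from the parent study Baseline to Week 52 and to Week 104 in predose concentrations of serum estradiol will be summarized". It adds the percentages of patients below 10 and below 20 pg/mL.

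**The concern.** Both the endpoint and its analysis depend on the sample being taken before that day's dose. Section 6.5.1.1 is where site staff would look for how to collect it. That section switches the condition off at one of the two extension time points, for a reason that three other places contradict. The passages on dosing cannot all be followed.

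If a site takes its dosing instruction from Section 5.4 and its sampling instruction from Section 6.5.1.1, nothing in those two sections requires blood to be drawn before the tablet and capsule, and the capsule contains 1 mg of oral estradiol. A postdose value would then enter a summary labelled predose, and the percentages below the two cut-offs would be affected as well.

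**Working it through.** No figure in the plan is in dispute, so the check is a comparison of passages.

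**Step 1: what each route through the text produces at Week 104.**

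| Route a site takes | Resulting sample |
|---|---|
| Footnotes w and o | Blood first, then the in-clinic dose: predose |
| Section 6.5.1.1 throughout, with no dose that day | About one dosing interval after the previous daily dose: trough-like, though not formally predose |
| Dose from Section 5.4 or the schedule row, sampling from Section 6.5.1.1, footnote o missed | Order left open: may be postdose |
| Section 6.5.1.1 read as no clinic dose, and the patient takes her usual morning dose at home, contrary to Section 5.4 | Postdose |

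The first two routes follow a coherent set of instructions, and both give an acceptable trough. The last two need a site to overlook footnote o or Section 5.4.

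**Step 2: how easily footnote o is missed.** In the Amendment 2 schedule the pharmacodynamics row carries superscript o, which is correct. In the later schedule it carries p, and footnote p is the eDiary text. Neighbouring rows show the same shift: the eDiary row carries q, although its footnote is p, and the bone densitometry row carries r, although its central-reading footnote is q. A reader who follows the superscript does not reach the one rule that keeps the sample predose.

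**Step 3: Early Termination.** Section 6.3 makes these procedures identical to Week 104, so an estradiol sample is taken. Section 4.5 (liver tests) and Section 7.8 (pregnancy) have treatment stopped at once, so some patients reach this visit already off drug and their samples cannot be predose. That would be so however the dosing conflict is settled. The pharmacodynamic endpoint names Week 52 and Week 104 only, whereas the primary efficacy endpoints name Week 104/Early Termination.

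**Step 4: can sample timing be verified?** Section 6.5.1.2 has dose date and time entered in the eDiary daily to Week 52, then in Weeks 57–65, 71–78, 85–91 and 98–104. The last cycle covers Week 104. The gaps after Week 52 are (57 − 52) + (71 − 65) + (85 − 78) + (98 − 91) = 5 + 6 + 7 + 7 = 25 of 52 weeks. The diary could therefore lack a dose time for an Early Termination in a gap, but not for a Week 104 visit with a completed diary.

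**Step 5: size.** Section 4.2 reports that a 6-week study in healthy women kept estradiol at 25 to 50 pg/mL on this add-back dose. The lower end is 25/20 = 1.25 times the upper cut-off and 25/10 = 2.5 times the lower one. Timing is thus more likely to matter for the 20 pg/mL percentage. The document gives no concentration-time profile and no expected number of mistimed samples, so no shift can be calculated.

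**The case against.** The strongest reply is that footnote o already settles the order of sample and dose. It names pharmacodynamics samples in its own words, and its preceding sentence concerns the Week 104/Early Termination sample. A site that reads it will draw blood first whether or not a dose follows. Both coherent readings then give a trough-like value, and a postdose draw would depart from the protocol.

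That reply stands as to what the protocol prescribes. It does not remove the conflict over whether a dose is given. It also does not explain why the procedural section exempts this visit from a condition that the footnote and the endpoint both impose.

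A reader might infer something stronger: that the Week 104 summary will mix predose, postdose and washed-out samples. The document does not support this. Postdose draws are not prescribed. Washed-out samples arise at Early Termination after treatment has stopped, not in a patient still dosing daily at Week 104. Nothing shown pools Early Termination estradiol into Week 104. Visit mapping is commonly left to the SAP, which is not at hand, so its absence here is not a fault.

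**Conclusion.** The contradiction is real and stands in operative text. Section 6.5.1.1 disagrees with footnote w, Section 5.4 and the in-clinic dosing row on whether a dose is given, and its exemption disagrees with footnote o and with the endpoint definition. What follows is a modest risk of mistimed samples at some sites, not a prescribed error.

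The reach is one of two extension time points of a descriptive pharmacodynamic endpoint with no test or decision rule attached. The primary efficacy endpoints and the comparison of lumbar spine bone mineral density with −2.2% do not use these samples.

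Two assumptions apply. The superscripts in the later schedule are taken as they were read from the PDF and should be checked against the source table. Section 9.6 of the later text is taken to match Amendment 2; the later synopsis states the same endpoint.

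**What to change.** 1. Reconcile Section 6.5.1.1 with footnote w, Section 5.4 and the in-clinic dosing row on whether a dose is given at Week 104 and at Early Termination, including for patients whose treatment has already been stopped. Which rule applies is for the sponsor to decide.
2. Remove the predose exemption from Section 6.5.1.1 and state that the sample is drawn before any study drug is taken that day. This wording works under either dosing rule and matches footnote o and the endpoint.
3. Correct the superscript on the pharmacodynamics row from p to o, and check the neighbouring rows for the same shift.
4. Unless the SAP already does so, restrict the Week 104 predose summary to samples that meet the definition, so that off-treatment Early Termination samples are listed separately and not counted as Week 104 predose values.

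The cost is a clarification letter or a few lines in the next amendment, and one SAP sentence. The Week 104 check needs no new data item, because the last eDiary cycle records dose times up to that visit.

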#### **6.5.1.2. Patient eDiary**

All women enrolled in the study will continue to use the patient eDiary dispensed in the parent study (see Appendix 2). Patients will complete daily eDiary entries, including NRS pain scores, menstruation information, analgesic drug use, date and time of study drug administration, and sB&B scale scores until Week 52. After Week 52, eDiary scores will be entered over four eDiary collection cycles on the following schedule: Week 57 to the Week 65 visit, Week 71 to the Week 78 visit, Week 85 to the Week 91 visit, and Week 98 to the Week 104 visit.

The site should review the eDiary data at every visit.

#### **6.5.1.3. Endometriosis Health Profile-30**

The EHP-30 is used to evaluate the functional impact and the quality of life of patients with endometriosis (see Appendix 3). Patients will complete the EHP-30 questionnaire at the site at visits indicated in Section 1.1 before other types of study procedures, such as blood draws and physical examinations, are performed. The EHP-30 will be completed on a tablet device at the study site.

#### **6.5.1.4. European Quality of Life Five-Dimension Five-Level Scale**

The EQ-5D-5L is a standardized instrument for use as a measure of health outcomes (see Appendix 4). Mobility, self-care, usual activities, pain/discomfort, and anxiety/depression are each assessed on a 5-level categorical scale.

Patients will complete the EQ-5D-5L questionnaire at the site at visits indicated in Section 1.1 before other types of study procedures, such as blood draws and physical examinations, are performed. The EQ-5D-5L will be completed on a tablet device at the study site.

#### **6.5.1.5. Patient Global Assessment and Patient Global Impression of Change**

These simple questions are used by the patient to qualitatively describe severity of pain or effects on function (PGA) or impression of change in pain severity (PGIC) (see [Appendix 5](#)) on a schedule described in the Schedule of Activities (Section 1.1). Patients should answer these questions before other types of study procedures, such as blood draws and physical examinations, are performed. The PGA for pain severity and the PGIC will be completed on a tablet device at the study site. The PGA for function will be completed on a paper questionnaire at the study site.

#### **6.5.1.6. Endometriosis Health Profile Work Domain**

This 5-question paper questionnaire will be completed by the patient to describe the effects of endometriosis on their work ([Appendix 6](#)). Patients will complete the EHP Work Domain questionnaire at visits indicated in Section 1.1 before other types of study procedures, such as blood draws and physical examinations, are performed. The EHP Work Domain will be completed on a paper questionnaire at the study site.

### **6.5.2. Safety-Related Procedures**

#### **6.5.2.1. Weight**

Patients should have weight and height measured while wearing indoor clothing and with shoes removed.

#### **6.5.2.2. Vital Signs**

Vital signs, including blood pressure, heart rate, and temperature, should be measured in the seated position after 5 minutes of rest.

#### **6.5.2.3. Physical Examinations**

A complete physical examination will include head, ears, eyes, nose, mouth, thyroid, skin, heart and lung examinations, lymph nodes, gastrointestinal, skeletal, and neurological systems. All subsequent physical examinations should focus on signs and symptoms reported by the patient to assess for clinically significant changes from the Baseline assessment. The physical examinations at Week 52 and Week 104 will include a breast examination.

#### **6.5.2.4. Clinical Laboratory Samples**

All protocol-required laboratory assessments must be conducted in accordance with the Investigator Site File and the protocol Schedule of Activities (see Section 1.1). Laboratory requisition forms must be completed and samples must be clearly labelled with the Patient ID number, protocol number, site/center number, and visit date. Details for the preparation and shipment of samples will be provided. Reference ranges for all safety parameters will be provided to the site by the central laboratory.

The samples collected for clinical laboratory tests are listed in [Table 6-1](#).

**Table 6-4 Clinical Laboratory Tests**

Chemistry	Hematology	Urinalysis
Potassium	White blood cell count	Protein
Chloride	White blood cell differential	Glucose
Bicarbonate	Red blood cell count	Blood
Blood urea nitrogen	Hemoglobin	Urobilinogen
Creatinine	Hematocrit	Bilirubin
Glucose	Mean corpuscular volume	Color and clarity
Calcium	Platelet count	pH
Phosphate	Red blood cell morphology	Leucocyte esterase
Magnesium		Ketones
Sodium		Nitrite
Albumin		Specific gravity
Creatine kinase		Urine microscopy (reflex testing based on abnormal urine analysis)
Hemoglobin A1c		
Bilirubin total		
Alanine aminotransferase		
Aspartate aminotransferase		
Gamma-glutamyl transferase		
Alkaline phosphatase		
Hormones	Lipids	Pregnancy
Estradiol	Total cholesterol	Pregnancy test (human chorionic gonadotropin)
	Low-density lipoprotein	
	High-density lipoprotein	
	Triglycerides	

The central laboratory will perform laboratory tests for chemistry, hematology, urinalysis, and serum hormone levels. Each study site will conduct urine pregnancy tests locally.

All laboratory tests with values that are considered abnormal and clinically significant during participation in the study or within 30 days after the last dose of study drug should be repeated until the values return to normal, baseline, or have stabilized. Abnormal values, determined to be clinically significant, should be reported as adverse events.

For patients with incomplete recovery of bone mineral density loss at the 6- and 12-month post-treatment follow-up visit, clinical laboratory tests should be performed (see Section 6.5.2.6).

The investigator will maintain a copy of the reference ranges (with the record of the reference ranges) for the laboratory or laboratories used.

#### 6.5.2.5. Electrocardiograms

Electrocardiograms (12-lead) will be obtained at the time points described in the Schedule of Activities (Section 1.1). Electrocardiograms will be measured using standardized equipment provided by the central core laboratory with the patient in a semi-supine or supine position after 5 minutes of rest. The ECGs will be assessed by central review and a report provided to the site. The investigator or sub-investigator (or a qualified individual at the investigational site) will interpret the ECG report provided by the central reviewer using one of the following categories: normal or abnormal. The investigator or sub-investigator will judge if any of the findings are clinically significant.

#### 6.5.2.6. Bone Mineral Density

Bone mineral density is determined using DXA scanning and will be assessed at the lumbar spine (L1, L2, L3, and L4), total hip, and femoral neck (same leg within each patient) at the time points described in the Schedule of Activities (Section 1.1). The scan will be read by the central imaging laboratory in accordance with the imaging charter. Training, quality review, and readings will be done by a central radiology laboratory as described in the central radiology charter for bone mineral density.
